5.2.5 Drug Attitude Inventory (DAI-10)

The DAI-10 contains 6 items (1, 3, 4, 7, 9, and 10) that a subject who is fully adherent to the prescribed medication would answer as "True", and 4 items (2, 5, 6, and 8) that a subject who is fully adherent to the prescribed medication would rate as "False." A correct answer is scored +1 and an incorrect answer is scored -1. The total score ranging from -10 to 10 (increment by 2) is the sum of pluses and minuses. A positive total score indicates a positive subjective response (adherent) and a negative total score indicates a negative subjective response (non-adherent). Higher scores denote better adherence. The total score will be considered as missing if at least one item score is missing.

5.2.6 Karolinska Sleepiness Scale (KSS)

The KSS is a scale that measures the subject's drowsiness and is frequently used in studies measuring subjective sleepiness. Scoring is based on a 9-point verbally anchored scale going from "1 = extremely alert" to "9 = very sleepy, great effort to keep awake, fighting sleep". Higher scores denote more drowsiness. Missing scores will not be imputed.

5.2.7 Massachusetts General Hospital Sexual Functioning Index (MGH-SFI)

Sexual functioning will be assessed using the MGH-SFI at Baseline (Study Week 0) and the MGH-SFI (follow-up version) at Study Weeks 5 and 10. MGH-SFI is a questionnaire that quantifies sexual dysfunction into 5 functional domains ("interest in sex," "sexual arousal," "ability to achieve orgasm," "ability to maintain erection" [males only], and "sexual satisfaction"). Subjects rate each item using a 6-point scale ranging from 1 (greater than normal) to 6 (totally absent). MGH-SFI (follow-up version) asks one more question (in addition to the 5 functional domains in MGH-SFI) on "overall improvement since your last medication change". Subjects rate this item using a 6-point scale ranging from 1 (very much improved) to 6 (much worse). Higher scores denote worse sexual dysfunction.

The MGH-SFI score to be analyzed will be calculated as the arithmetic mean of the item scores for the 5 domains and rounded to the nearest 2 decimal places. For MGH-SFI at Baseline (Study Week 0), the arithmetic mean will be calculated over all 5 domains for males and the 4 domains for females. For MGH-SFI (follow-up version) at Study Weeks 5 and 10, the arithmetic mean will be calculated in the same way as MGH-SFI at Baseline excluding the item score for the additional domain of "overall improvement since your last medication change". The MGH-SFI arithmetic mean score will be considered as missing if at least one item score is missing.

5.2.8 Barratt Impulsiveness Scale (BIS-11)

The BIS-11 is a questionnaire designed to assess the personality/behavioral construct of impulsiveness. It is composed of 30 items describing common impulsive or non-impulsive (reverse scored items: 1, 7, 8, 9, 10, 12, 13, 15, 20, 29, and 30) behaviors and preferences. Items are scored on the following 4-point scale: Rarely/Never = 1; Occasionally = 2; Often = 3; Almost Always/Always = 4. For reverse scored items, a response of 1 is recoded to 4; 2 is recoded to 3; 3 is recoded to 2; and 4 is recoded to 1. The BIS-11 score ranging from 30 to 120 will be calculated as the sum of the scores for all 30 items. Higher scores denote more impulsiveness. Missing item scores will be imputed with the arithmetic mean of the non-missing item scores and rounded to the nearest integer. The BIS-11 score will be considered as missing if there are missing scores for 7 or more items.

5.2.9 Sheehan Irritability Scale (SIS)

The SIS is a 7-item subject-reported outcome measure that was developed to measure the frequency, severity, and impairment associated with irritability in psychiatric subjects. It includes items on: irritability, frustration, edginess/impatience/overreaction, moodiness, anger with self, anger with others, and temper. The recall period is the past 7 days. Items are answered on an 11-point rating scale where higher scores indicate greater severity (0= not at all, 10= extremely). The total score ranging from 0 to 70 will be calculated as the sum of the scores for all 7 items. Missing item scores will be imputed with the arithmetic mean of the non-missing item scores and rounded to the nearest integer. The total score will be considered as missing if there are missing scores for 2 or more items.

5.2.10 Montgomery Asberg Depression Rating Scale (MADRS)

The MADRS is a 10-item, clinician-rated instrument measuring depression severity. It is scored on a fixed scale of 7 points (0-6) following a structured clinician interview. The total score ranging from 0 to 60 will be calculated as the sum of the scores for all 10 items. Higher scores reflect more severe symptomatology. The total score will be considered missing if there are at least one missing item scores.

5.3 Analysis Visit Windows

Baseline for Stage 1 of the study is defined as the last non-missing result, including results from repeated and unscheduled measurements, before first dosing in Stage 1. Baseline for subjects randomized into Stage 2 is defined as the results at Study Week 5.

Statistical Analysis Plan
2018

21 August

Efficacy, safety, and PK assessments will be summarized by analysis visit as presented in Table 2 below. For the Week 5 visit window only, the assessments collected on the date of randomization for the subjects who are randomized into Stage 2 will be selected for the analysis even if the Stage 2 randomization date is outside of the Study Day Interval, 33 - 39.

Table 2 Analysis Visit Windows

Analysis Visit	Study Visit	Target Study Day @	Study Day Interval
Baseline (Day 1 for Stage 1)	2 (Week 0)	1	≤ 1
Week 1	3 (Week 1)	8	2 – 11
Week 2	4 (Week 2)	15	12 – 18
Week 3	5 (Week 3)	22	19 – 25
Week 4	6 (Week 4)	29	26 – 32
Week 5	7 (Week 5)	36	33 – 39
Week 6	8 (Week 6)	43	40 – 46
Week 7	9 (Week 7)	50	47 – 53
Week 8	10 (Week 8)	57	54 – 60
Week 9	11 (Week 9)	64	61 – 67
Week 10	12 (Week 10)	71	68 – 78
Follow-up	~30-Day Follow-Up	101	≥79

@ Derivation of study day: study day = assessment date - first dose date + 1 if the assessment date ≥ first dose date, otherwise study day = assessment date – first dose date. Study day 1 is the day of first administration of study drug (pimavanserin or placebo).

Efficacy and safety assessments for Stages 1 and 2, when presented side by side or separately, will be summarized by analysis visit as presented in Table 3.

Table 3 Analysis Visit for Side-by-side or Separate Presentation of Stages 1 and 2

Data

Analysis Visit	Study Visit in Stage 1	Study Visit in Stage 2
Baseline (Day 1)	2 (Week 0)	7 (Week 5)
Week 1	3 (Week 1)	8 (Week 6)
Week 2	4 (Week 2)	9 (Week 7)
Week 3	5 (Week 3)	10 (Week 8)
Week 4	6 (Week 4)	11 (Week 9)
Week 5	7 (Week 5)	12 (Week 10)

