3.3.2 Stage 2 Double-blind Treatment Period

At the end of Stage 1 (Study Week 5), subjects initially randomized to placebo and who meet the non-responder criteria will be randomly assigned in a 1:1 ratio to pimavanserin or placebo. Subjects initially randomized to pimavanserin in Stage 1 will continue to receive pimavanserin through the end of Stage 2.

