5.3.1 Unscheduled Assessments

Both Scheduled and Unscheduled assessments, including the assessments at early termination visits, will be used for planned timepoint analyses. All assessments will be presented in data listings.

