5.3.2 Multiple Measurements within Visit Windows

In the event that more than one assessment falls within a given window the assessment closest to the target study day will be selected for the by-visit analysis. If two assessments are equidistant from the target study day then the chronologically last assessment will be used. Exceptions may be made for incomplete assessments, in which case, more complete assessments may be given priority. Details are provided in a separate programming conventions document.

For safety analyses where the extreme values should be selected (e.g. overall post-Baseline minimum, overall post-Baseline maximum, and overall post-Baseline potentially clinically important values), all non-missing post-Baseline values should be considered, regardless of whether the value is selected for the by-visit summaries. All assessments will be presented in data listings.

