12.3 Handling of Missing Data

The primary analyses of the primary and key secondary efficacy endpoints will be performed in 2 steps and the missing data issue is only involved in Step 1:

1. Data from Stages 1 and 2 will be analyzed separately assuming missing at random (MAR) using the stage-specific, direct likelihood-based MMRMs and scores that are missing, after any imputation of individual missing items as described in Sections 5.2.1 and 5.2.2, will not be imputed. The MMRM method is unbiased under the MAR assumption and can be thought of as aiming to estimate the treatment effect that would have been observed if all subjects had continued on treatment for the full study duration (EMA, 2009).
2. Weighted combination of statistics from the stage-specific MMRMs will be used to perform the hypothesis testing.

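### SAP 5.3 keeps an off-window Week 5 score only for re-randomised placebo non-responders: a small, avoidable outcome-dependent selection if Table 2's day windows feed the Stage 1 MMRM

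*SAP*

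**What the plan says.** SAP section 5.3 contains two visit tables. Table 2 allocates assessments by study day: Week 4 is days 26–32, Week 5 is 33–39 and Week 6 is 40–46. For Week 5 alone there is an exception: "the assessments collected on the date of randomization for the subjects who are randomized into Stage 2 will be selected for the analysis". It overrides the 33–39 interval when that date lies outside it. Table 3 lists visit numbers without day intervals. It covers Stage 1 and Stage 2 efficacy and safety data which, "when presented side by side or separately, will be summarized by analysis visit as presented in Table 3".

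On who is randomised into Stage 2, section 3.3.2 says: "subjects initially randomized to placebo and who meet the non-responder criteria will be randomly assigned in a 1:1 ratio". Section 3.1 defines non-response as a Week 5 HAMD-17 above 14 with a reduction from Week 0 of less than 50%.

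Three further rules bear on the point:

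- Section 5.3.1: "Both Scheduled and Unscheduled assessments, including the assessments at early termination visits, will be used for planned timepoint analyses".
- Section 5.3.2: where several assessments fall in one window, "the assessment closest to the target study day will be selected for the by-visit analysis". Further detail is left to a programming conventions document.
- Section 5.3, on the second stage: "Baseline for subjects randomized into Stage 2 is defined as the results at Study Week 5".

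Section 12.3 rests the stage-specific MMRMs on missing at random (MAR).

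**The concern.** On the Table 2 reading, the exception can never apply to a pimavanserin subject, or to a placebo subject who improved enough not to be re-randomised. Their off-window Week 5 score moves to the Week 4 or Week 6 window. Week 5 is then empty, or is filled by a neighbouring visit that happens to fall in days 33–39.

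Dependence on arm alone would be compatible with MAR, because treatment is in the model. The difficulty is within placebo, where an off-window score is kept or moved according to that score. Weeks 1–4 recover only part of what is lost. If visit timing is unrelated to outcome, good placebo scores drop out and poor ones stay. Placebo then looks worse than it was, and the Stage 1 difference moves towards pimavanserin.

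The sensitivity analyses in section 13.1.2 are unlikely to show this. The per-protocol analysis repeats the primary method, and the pattern-mixture analysis imputes from the observed placebo data, which on this reading are the selected data.

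The exception has a proper purpose, since the Study Week 5 result is the Stage 2 baseline. What it lacks is a counterpart for everyone else. Sections 7, 11 and 14.1 each pair the Stage 2 randomisation date with the Study Week 5 visit date for subjects not re-randomised; section 5.3 gives only the first half.

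**Working it through.** **Inputs from SAP 3.5.** 168 evaluable subjects at 1:3, so 42 pimavanserin and 126 placebo. Stage 1 changes are −10 and −7.8 (difference 2.2, SD 8). Stage 2 changes are −6.0 and −2.8 (difference 3.2, SD 6). Weights are 0.5/0.5 and placebo non-response is 70%, so 0.70 × 126 ≈ 88, or 44 per arm in Stage 2.

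**Reproducing the plan's power.**

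- Weighted effect = 0.5 × 2.2 + 0.5 × 3.2 = 2.7.
- SE = 0.5 × √[64 × (1/42 + 1/126) + 36 × (2/44)] = 0.5 × √(2.032 + 1.636) = 0.958.
- Power = Φ(2.7/0.958 − 1.96) = 80.5%, as stated (at least 80%).
- 168/0.9 = 186.7, so 187, against the stated 188 (a multiple of 4).

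**Subjects affected.** The documents give no off-window share *f*, so it is assumed. Placebo subjects not re-randomised number 0.30 × 126 = 37.8. At *f* = 5–10%, 1.9–3.8 of them lose the Week 5 score, as do 2.1–4.2 of the 42 pimavanserin subjects. No re-randomised subject does.

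**Complete-case shift.** Treat placebo change as normal (−7.8, SD 8) and the best 30% as not re-randomised. The two parts have means −17.07 and −3.83. After the loss,

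placebo mean = [0.3(1 − f)(−17.07) + 0.7(−3.83)] / [0.3(1 − f) + 0.7].

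At *f* = 5% this is −7.66, a shift of 0.14; at 10% it is −7.51, a shift of 0.29.

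**MMRM shift, moved scores treated as missing.** Large-sample maximum likelihood, unstructured covariance, no true effect, AR(1) correlation of 0.6, 0.8 or 0.9 (assumed). Half of the shift enters the weighted estimate, and two-sided type I error = P(|Z + bias/SE| > 1.96).

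| f | Complete-case shift | Stage 1 MMRM shift | Weighted shift | Type I error |
|---|---|---|---|---|
| 2% | 0.06 | 0.01–0.04 | 0.005–0.02 | 0.050 |
| 5% | 0.14 | 0.03–0.09 | 0.01–0.05 | 0.050 |
| 10% | 0.29 | 0.05–0.19 | 0.03–0.09 | 0.050–0.051 |
| 20% | 0.59 | 0.11–0.39 | 0.06–0.19 | 0.050–0.055 |

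All shifts favour pimavanserin. At 10% the tail favouring the drug is 0.027–0.031 instead of 0.025. Applying the literal non-responder rule with an assumed baseline mean of 22 or 26 changes little (largest weighted shift 0.10 at 10%).

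**MMRM shift with visits actually reassigned by Table 2.** Simulation, 400,000 subjects per scenario, 16 scenarios, Stage 1 difference 0 or −2.2. Assumed:

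- baseline SD 4, with mean 26.6 so that the literal rule gives 70% non-response, and slope of change on baseline −0.3;
- SD of change 5, 6.2, 7, 7.6, 8 and 8 at Weeks 1–6, adjacent-visit correlation 0.68 or 0.80;
- visit day = target plus rounded normal error, with timing correlation between adjacent visits of 0 or 0.85;
- visit gaps of 1–12 days (the 10-day kit of Protocol 5.1.1 plus 2 missed doses, Protocol 5.1.5).

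| Rule applied | Stage 1 shift, f = 5% | Stage 1 shift, f = 10% |
|---|---|---|
| Table 2 with the exception | 0.04–0.07 | 0.08–0.16 |
| Windows applied to placebo only | 0.04–0.07 | 0.07–0.15 |
| Windows applied to pimavanserin only | −0.01 to 0.01 | −0.01 to 0.01 |
| Table 2 without the exception | −0.01 to 0.01 | −0.01 to 0.01 |

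The weighted shift is 0.02–0.03 at 5% and 0.04–0.08 at 10%. Among off-window subjects without the exception, 4–12% (independent timing) or 50–56% (correlated timing) still had another value in days 33–39. The bias comes from the selection within placebo. Losses that are not selective add almost nothing.

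**The case against.** The strongest objection is that Table 2 may not govern the MMRM at all. Section 12.3 analyses the stages separately, which fits Table 3's scope. The primary endpoint is labelled Baseline to Week 5 in both stages, and only Table 3 carries a Stage 2 Week 5. The exception also has other work to do: it fixes the Stage 2 baseline, and it serves the 10-week summaries in sections 12 and 14, which include subjects re-randomised from placebo to placebo. Part of 13.1.1 is redacted and some detail sits in a programming document, so the deciding text may exist unseen.

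This stands as a condition on the finding, but it does not settle the matter for Table 3. The exception speaks of scores chosen for the analysis, and unscheduled and early-termination scores are used at planned timepoints, for which Table 3 has no day rule. Table 3 could also be read as merely relabelling Table 2's windows by stage.

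Second, the off-window share is assumed. The protocol's visit window is ±3 days, which is exactly days 33–39 around target day 36, so an off-window visit is already outside the schedule and should be uncommon. That is fair, and the 2% row shows how little then remains. The direction likewise assumes that visit timing is unrelated to outcome.

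Third, sections 7, 11 and 14.1 assign events, deviations and medications to stages and do not select efficacy scores. The comparison with 5.3 is therefore an analogy, not an inconsistency.

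None of this removes the asymmetry in the written rule.

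**Conclusion.** The point holds, conditionally, and is minor. If Table 2's windows feed the Stage 1 MMRM, section 5.3 makes the availability of the primary value within placebo depend on that value, contrary to the MAR assumption. Over both MMRM calculations, the Stage 1 shift towards pimavanserin is 0.03–0.09 points at 5% off-window and 0.05–0.19 at 10%. Even the largest weighted shift at 10%, 0.10, is about a tenth of the SE (0.10/0.958) and under 4% of the planned effect (0.10/2.7), and two-sided type I error does not exceed 0.051.

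These sizes rest on the assumed off-window share, visit correlations, baseline values and timing. If Table 3 means nominal visits and governs, the bias is zero. For response and remission (section 13.3), a missing score counts as failure, so the same rule would lower both arms' rates and is not claimed to favour either.

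The reason to act is that the rule sits in the primary analysis, errs towards the test drug on the natural timing assumption, and can be removed by wording.

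**What to change.** In SAP 5.3, for every FAS1 subject, take the score at the nominal Study Week 5 visit (visit 7) as the Stage 1 Week 5 value, whatever the study day, arm or re-randomisation status. Do not also assign that score to the Week 4 or Week 6 window. Where there is no visit 7, as with earlier withdrawals whose last scores are taken at the Week 10/ET visit, apply Table 2 to all subjects alike. State that this rule governs the stage-specific MMRMs, and keep the randomisation-date score as the Stage 2 baseline.

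Add a line on a neighbouring visit that falls in days 33–39 but is displaced by visit 7. Any rule applied alike to all subjects will do.

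If nominal visits were always intended, one sentence saying that Table 3 governs the MMRMs closes the point.

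The cost is SAP wording and programming. The visits are already collected, and planned power stays at 80.5%. Subjects who withdrew before Week 5 and the Stage 2 baseline are unaffected.

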5.3.1 Unscheduled Assessments

Both Scheduled and Unscheduled assessments, including the assessments at early termination visits, will be used for planned timepoint analyses. All assessments will be presented in data listings.

5.3.2 Multiple Measurements within Visit Windows

In the event that more than one assessment falls within a given window the assessment closest to the target study day will be selected for the by-visit analysis. If two assessments are equidistant from the target study day then the chronologically last assessment will be used. Exceptions may be made for incomplete assessments, in which case, more complete assessments may be given priority. Details are provided in a separate programming conventions document.

For safety analyses where the extreme values should be selected (e.g. overall post-Baseline minimum, overall post-Baseline maximum, and overall post-Baseline potentially clinically important values), all non-missing post-Baseline values should be considered, regardless of whether the value is selected for the by-visit summaries. All assessments will be presented in data listings.

5.4 Missing or Incomplete Date for Last Dose of Study Drug

In the Safety Analysis Set, if the last dose date of study drug is missing for a subject who completed or early terminated from the study, then the date of the end-of-study/early termination visit will be used in the calculation of treatment duration. For the incomplete last dose date of study drug, the imputation algorithms will be detailed in the analysis dataset specification document. The missing or incomplete dates will be displayed in the data listings as reported on the eCRF rather than the imputed dates.

5.5 Missing or Incomplete Dates for Prior or Concomitant Medications

Missing or incomplete medication start or stop dates will be imputed for the purpose of determining whether the medication is taken concomitantly or not (see Section 11 for definition). When the chronological order of medication use relative to the study drug treatment period is unclear due to missing or incomplete date(s), the medication will be considered as concomitant. The imputation algorithms will be detailed in the analysis dataset specification document. The missing or incomplete dates as captured on the eCRF will be displayed in the data listings.

5.6 Missing or incomplete Date for Adverse Events

Missing or incomplete adverse event (AE) start dates will be imputed for the purpose of determining whether the AEs are treatment-emergent or not (see Section 14.1 for definition). When the chronological order of an AE onset relative to the study drug treatment period is unclear due to missing or incomplete date(s), the AE will be considered as treatment-emergent. The imputation algorithms will be detailed in the analysis dataset specification document. The missing or incomplete dates captured on the eCRF will be displayed in the data listings.

5.7 Missing Severity Assessment for Adverse Events

If the severity is missing for an AE starting on or after the date of the first dose of study drug, then a severity of “Severe” will be assigned. The imputed values for severity assessment will be used for incidence summaries, while the actual values will be used in data listings.

5.8 Missing Relationship to Study Drug for Adverse Events

If the relationship to study drug is missing for an AE starting on or after the date of the first dose of study drug, a causality of “Related” will be assigned. The imputed values for

relationship to study drug will be used for incidence summaries, while the actual values will be presented in data listings.

5.9 Character Values of Clinical Laboratory Variables

If the reported value of a clinical laboratory variable cannot be used in a statistical analysis due to, for example, a character string reported for a numeric variable, an appropriately determined coded value may be used in the statistical analysis. The coding algorithms will be detailed in the analysis dataset specification document. The actual values as reported in the database will be presented in data listings.

6. SUBJECT DISPOSITION

For subjects who participate in the screening phase but are not randomized (screen failures), their demographics information (including age, sex, and primary race), screen failure reasons (the specific inclusion/exclusion criterion (or criteria) not met or other reason) and protocol version will be listed. If a subject is re-screened, then the re-screening subject ID and the final enrollment status (whether eventually enrolled) will also be displayed in this listing. In addition, the frequency that the screen failure reasons are reported will also be summarized. Note that one subject may be deemed ineligible for multiple inclusion/exclusion criteria and may be allowed to rescreen with the permission of the Medical Monitor, provided the screen failure was due to a temporary condition that subsequently resolved.

Subject disposition will be summarized to show the number of subjects screened, randomized by treatment group and stage, received study drug by treatment group and stage, discontinued by reason and treatment group and stage, and completed study by treatment group and stage.

Reasons for discontinuation will be summarized by treatment arm and overall for RAS1 and RAS2; SAS1 and SAS2; and FAS1 and FAS2. A listing will be provided displaying all subjects excluded from the Safety, Full or Per-protocol analysis sets, and will include reason(s) for exclusion.

The number of subjects screened, the number of unique subjects screened, the number of subjects randomized into Stage 1, and the number of subjects randomized into Stage 2 will be summarized overall and by site. The number of subjects enrolled at each site will also be tabulated by treatment arm and overall for RAS1 and RAS2; SAS1 and SAS2; FAS1 and FAS2; and PAS1 and PAS2.

